4. CHANGES IN THE PLANNED ANALYSIS OF THE STUDY

4.1 CLARIFICATIONS

As this trial is the first in human use of BI 836826, the primary objective as defined by the Clinical Trial Protocol (CTP) is to determine the maximum tolerated dose (MTD) of BI 836826. The MTD is determined via the number of dose limiting toxicities (DLTs). The CTP does not contain any definition of primary endpoint. But to follow the definition of the primary objective of the trial as defined by the CTP, the MTD and the number of patients with DLTs during the MTD evaluation period are defined as primary endpoints (see Section 5.1).

During the course of the trial it was decided to change the definition of some of the secondary and further endpoints:

1. Number of lymphocytes in the peripheral blood

The definition of this endpoint was changed from "Number of lymphocytes in the peripheral blood" to "Best % change from baseline in number of lymphocytes in the peripheral blood".

2. Blood counts (haemoglobin, platelets, neutrophils, red blood cells)

The definition of this endpoint was changed from "Blood counts (haemoglobin, platelets, neutrophils, red blood cells)" to "number of patients with improved haemoglobin count for at least two subsequent response assessments", "number of patients with improved platelet count for at least two subsequent response assessments" and "number of patients with improved neutrophil count for at least two subsequent response assessments". It was decided to abandon the definition of a separate secondary endpoint for red blood cells, since red blood cells are highly correlated with haemoglobin count and are thus reflected in this endpoint.

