5.2.2 Other Secondary endpoints

Note: For the response/efficacy analyses with respect to overall response assessment by investigator used: If patients would have their examinations contributing to the disease assessment over a number of days, the earliest date of the multiple examinations should be considered.

For the response/efficacy analyses with respect to lymphocytes and blood counts only laboratory data assessed >= 8 days after the last infusion and with reported laboratory response assessment on-treatment and before start of new Chronic Lymphocytic Leukaemia (CLL) therapy is used. The reason for this approach is that otherwise the respective values of lymphocytes and blood counts would be biased due to the infusion after which an immediate change in values of the respective blood parameters is observed. This change though does not reflect an efficacy effect.

Number of lymphocytes in the peripheral blood

The secondary endpoint with respect to number of lymphocytes in the peripheral blood is defined as "Best % change from baseline in number of lymphocytes in the peripheral blood".

Blood counts (haemoglobin, platelets, neutrophils)

The secondary endpoints with respect to blood counts are defined as

- "Number of patients with improved haemoglobin count for at least two subsequent response assessments"
- "Number of patients with improved platelet count for at least two subsequent response assessments"
- "Number of patients with improved neutrophil count for at least two subsequent response assessments"

An improvement is indicated by the fulfilment of the criteria for "Complete Remission" or "Partial Remission", i.e.

- Haemoglobin count: Greater than 11g/dL or increase of 50% or more compared to baseline if haemoglobin is less than or equal to 11g/dL
- Platelet count: Greater than 100 000/ μ L or increase of 50% or more compared to baseline if platelets are less than or equal to 100 000/ μ L
- Neutrophil count: Greater than 1500/ μL or increase of more than 50% compared to baseline if neutrophil count is less than or equal to $1500/\mu L$

Best overall response:

Response will be assessed according to the NCIWG guidelines (R10-4429) based on laboratory data from the peripheral blood and clinical examination by the investigator. Each patient will be assigned to one of the following categories:

- complete remission (CR)
- complete remission with incomplete marrow recovery (CRi)
- partial remission (PR)
- stable disease (SD)

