7.5.2 Secondary endpoints

Number of lymphocytes in the peripheral blood

The number of lymphocytes in the peripheral blood will be analyzed in terms of the best percentage change from baseline until start of subsequent CLL therapy or PD. Best percent change is thereby derived by taking the difference between the baseline value and the minimum of all observed values over time. For the primary analysis of this endpoint, summary statistics will be presented for all patients of the TS by dose cohort and in total. In addition, summary statistics will be presented separately for patients of the TS with an abnormal and normal lymphocyte count at baseline. An abnormal baseline count is defined as a lymphocyte count $> 4*10^9$ /L. In addition, the following will be analysed:

Summary statistics will additionally be presented for minimum values of certain lymphocyte types (CD19+ B-cells, CD3+ T-cells, CD4+ T-cells, CD8+ T-cells and CD56+ NK-cells).

For CD4+ T-cells and CD19+ B-cells, the lowest count since start of treatment (nadir) and the time point of occurrence of (nadir) will be derived and described by summary statistics for all dose cohort together and separated by dose cohort. The association of values at baseline and values at nadir will be displayed graphically.

A waterfall plot will also be generated to summarise reduction of lymphocytes graphically and lymphocyte values will be graphically displayed over time for patients of the Treated Set. Furthermore, the number of lymphocytes and the change in lymphocyte count from baseline will be listed by time point.

Blood counts (haemoglobin, platelets, neutrophils)

[figure not shown]
A frequency table will be given for the endpoints "Number of patients with improved haemoglobin / platelet / neutrophil count for at least 2 subsequent response assessments" for all patients of the Treated Set. Additionally, graphical presentations of mean values of haemoglobin, platelet and neutrophil counts over time will be provided by dose cohorts. For neutrophils, the nadir and the time point of occurrence of nadir will be derived and described by summary statistics for all dose groups together and separated by dose group. The association of values at baseline and at time to nadir will be displayed graphically.

[figure not shown]
Best overall response

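### SAP 7.5.2 takes the best lymphocyte change from all observed values, against the 8-day rule in SAP 5.2.2, and leaves the percent formula incomplete

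*SAP*

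**What the plan says.** SAP 4.1 records that the secondary endpoint on lymphocyte number was changed to "Best % change from baseline in number of lymphocytes in the peripheral blood", and 5.2.2 repeats that definition.

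SAP 5.2.2 opens with a data rule for the efficacy analyses of lymphocytes and blood counts. They use "only laboratory data assessed >= 8 days after the last infusion and with reported laboratory response assessment on-treatment", and only before new CLL therapy starts. The section explains that counts change immediately after an infusion and adds: "This change though does not reflect an efficacy effect".

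SAP 7.5.2 says the endpoint is "analyzed in terms of the best percentage change from baseline until start of subsequent CLL therapy or PD". The next sentence gives the derivation: "Best percent change is thereby derived by taking the difference between the baseline value and the minimum of all observed values over time". It does not repeat or cite the 8-day rule. The result is summarised for the Treated Set by dose cohort and in total, and a waterfall plot of lymphocyte reduction is planned.

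Protocol 7.3.2.1 plans the maximal reduction over every time point after baseline, with no 8-day limit.

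**The concern.** One secondary endpoint has two rules for which values count. A minimum is the summary most sensitive to that choice, because one early low value fixes the patient's result. A programmer working from the analysis section would admit the samples that the endpoint section calls biased. A programmer working from the endpoint section would exclude them. Each could point to SAP text.

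Two smaller gaps sit in the same place. The derivation sentence gives a difference with no division by baseline and no sign convention. The cut-off also differs: 7.5.2 names PD, whereas 5.2.2 names the on-treatment period and new CLL therapy and says nothing about PD for this endpoint.

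At stake is whether the cohort summaries and the waterfall plot show the effect that the SAP regards as efficacy, or that effect mixed with the immediate response to infusion.

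**Working it through.** The plan states no figure for this endpoint, so there is nothing to reproduce. Three checks follow.

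**1. Which scheduled samples each rule admits.** Inputs: course 1 infusions on days 1 and 2, or on days 1, 2 and 8, and day 1 only in later courses (protocol 4.1); a 14-day course and the visit days (Flow Charts and 10.6); blood counts at all visits (protocol 5.1.2.3). Days since infusion = sample day minus day of the last infusion before it.

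| Schedule | Sample day | Days since last infusion | At least 8? |
|---|---|---|---|
| Course 1, two portions | 2 | 0 or 1 (after or before that day's infusion) | no |
| | 3 | 3 − 2 = 1 | no |
| | 4 | 4 − 2 = 2 | no |
| | 8 | 8 − 2 = 6 | no |
| | 15, pre-dose | 15 − 2 = 13 | yes |
| Course 1, three portions | 8, pre-dose | 8 − 2 = 6 | no |
| | 9 | 9 − 8 = 1 | no |
| | 15, pre-dose | 15 − 8 = 7 | no |
| Later courses | 2 | 2 − 1 = 1 | no |
| | 3 (+2) | 2 to 4 | no |
| | 8, nominal | 8 − 1 = 7 | no |
| | 9 or 10, within the +2 window | 8 or 9 | yes |
| | 15, pre-dose | 15 − 1 = 14 | yes |

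Samples on days 9 and 10 of later courses pass the day count. However, the Flow Chart schedules no response assessment at that visit, so they would normally fail the second condition in 5.2.2. On schedule, the eligible on-treatment values are therefore mainly the pre-dose value of the next course and the EOT value. Under the literal 7.5.2 wording, every post-baseline row of the table counts.

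**2. What that does to the result.** Let B be baseline, E the lowest value within 8 days of an infusion, and L the lowest eligible later value. All counts below are assumed (×10⁹/L).

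- All values: 100 × (min(E, L) − B) / B
- Eligible values only: 100 × (L − B) / B
- Gap in percentage points: 100 × (L − E) / B if E is below L, otherwise 0

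| B | E | L | All values | Eligible only | Gap |
|---|---|---|---|---|---|
| 50 | 5 | 20 | 100 × (5 − 50)/50 = −90% | 100 × (20 − 50)/50 = −60% | 30 |
| 50 | 10 | 30 | 100 × (10 − 50)/50 = −80% | 100 × (30 − 50)/50 = −40% | 40 |
| 50 | 20 | 5 | −90% | −90% | 0 |

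With the same cut-off, the all-values result can only equal or exceed the eligible-only reduction, because its minimum runs over a larger set. Any discrepancy therefore goes one way, towards a larger apparent reduction.

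**3. Formula and cut-off.** In the first row, the difference in the 7.5.2 sentence is 50 − 5 = 45 ×10⁹/L. It becomes a percent change only after division by 50 and a choice of sign. On the cut-off, SAP 7.8.1.2 ends the on-treatment period 6 weeks after the last administration, while protocol 6.2.3.2 continues follow-up for 6 months after EOT. The end of the on-treatment period, PD and new CLL therapy can thus be three different dates, and neither section lists all three.

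**The case against.** The best reply is that 5.2.2 is worded as a general filter for efficacy analyses of lymphocytes and blood counts. It is not confined to its own section, so all observed values in 7.5.2 would mean all eligible ones. That reading is plausible and probably intended. But 7.5.2 does not say so, and its wording is close to the protocol's unrestricted rule in 7.3.2.1, so the text also supports the other reading.

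The early fall stays visible in any case: 7.5.2 plots lymphocyte values over time and lists counts and changes by time point. This limits the harm but does not settle which number enters the summary table.

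A reader might infer more than the documents support:

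- *That 7.5.2 sets up a rival absolute-difference endpoint.* Sections 4.1, 5.2.2 and 7.5.2 itself all name a percent scale. The formula is incomplete; it does not compete.
- *That the windows contradict each other outright, one keeping values after PD and the other keeping late follow-up values.* Each section is only silent where the other speaks, and all the limits can apply together. What remains is a PD stop found in 7.5.2 alone.
- *That this is the main efficacy measure.* SAP 5.2.1 and 7.5.1 name no key secondary endpoint, and protocol 7.2 makes all analyses descriptive. The cohort-expansion trigger in protocol 3.1 concerns B-lymphocytes in course 1 and does not use this derivation.

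**Conclusion.** The derivation sentence in SAP 7.5.2 is wrong as written. It admits values that 5.2.2 excludes for a stated reason, and it stops short of a percent change. The missing PD stop in 5.2.2 is a smaller mismatch that should be settled in the same edit.

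The schedule check rests on the documents alone. The size does not: it depends on assumed counts and on the immediate post-infusion change being a fall, a direction 5.2.2 does not state. In the examples the gap is 0 points when the lowest value comes at least 8 days after infusion, and 30 to 40 points when an early low is followed by partial recovery. These are illustrations, not bounds or predictions.

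The consequence is confined to a descriptive secondary endpoint and its waterfall plot. MTD, DLT and sample size are unaffected.

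**What to change.** Replace the derivation sentence in SAP 7.5.2 with: best % change = 100 × (minimum eligible post-baseline value − baseline) / baseline, where eligible values meet the Section 5.2.2 rule and fall before the earliest of PD, start of subsequent CLL therapy, or end of the on-treatment period. State the same cut-off in 5.2.2, and say that the waterfall plot uses this value.

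Record in SAP Section 4 that the restriction departs from protocol 7.3.2.1. Section 4.1 notes the move to a percent change but not the 8-day limit.

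The cost is SAP wording; no new data are needed. The downside is that patients with no eligible value drop out of the summary. An example is a patient who stops within course 1 and whose EOT data are collected at once under protocol 6.2.3.1. Report their number by dose cohort next to the summary. If the immediate fall is also of interest, show it as a separately labelled pharmacodynamic summary over all post-baseline values.

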7.7 EXTENT OF EXPOSURE

Standard descriptive analyses over all treatment courses will be performed. This will include a summary of the variables already described in Section 5.4.2. This descriptive analysis will comprise a mixture of frequency and percentages, as well as summary statistics.

For the sequence of doses, there will be a listing of each dose taken at each treatment course for all patients.

7.8 SAFETY ANALYSIS

The primary analysis is for determination of MTD. No statistical model is foreseen allowing assessment of MTD; descriptive analysis is confined to a listing and descriptive table by dose group. The purpose of these tables is to summarize and document the data that led to the selection of MTD.

[figure not shown]
7.8.1 Adverse events

[figure not shown]

7.8.1.2 Adverse events

Unless otherwise specified, adverse events analysis will be performed for on-treatment periods. Selected analyses (e.g. summary of AEs) will be repeated for the MTD evaluation period.

The analyses of AEs will be descriptive in nature and will follow the standard procedure laid down in the DM & SM (including all required tables and listings; guideline _'Handling and Summarization of AE Data for CTR and Integrated Summaries' (4). AEs will be coded with the most recent version of Medical Dictionary for Regulatory Activities (MedDRA). The version number will be displayed as a footnote in the respective tables and listings.

The system organ classes will be sorted alphabetically. In tables displaying AEs by dose cohort preferred terms will be sorted by descending frequency of adverse events in the "Total" BI 836826 group.

Each patient can be observed during the trial under several doses. Analysing the AE of all treatment courses will be carried out under the initial treatment. No formal statistical analysis is planned for the safety comparison.

The analysis of AEs will be based on the concept of treatment emergent AEs. That means that all adverse events occurring between first administration of BI 836826 until 6 weeks after last administration of BI 836826 will be assigned to the on-treatment period. All adverse events occurring before first administration of BI 836826 will be assigned to "Screening" and all adverse events occurring after last administration of BI 836826 + 6 weeks will be assigned to "post-study (for listings only). The actual planned dosage of BI 836826 administered on the day each AE starts will also be derived and will be included in the listing. Listings of screening events will not be sorted by initial treatment. Post-study listings will be sorted by initial treatment. For details on the treatment definition please refer to Section 6.1.

According to the BI standards, multiple recordings of AEs will be collapsed to episodes on the lowest level term and multiple episodes will be condensed to records on the PT and system organ class (SOC) level. CTCAE grade will be an additional criterion for collapsing and condensing AEs. The maximum CTCAE grade will be assigned to episodes and records. CTCAE grade and DLT information will be displayed in AE listings. MedDRA levels for condensing will be SOC and PT.

An overall summary of adverse events will be presented.

Reporting of CTCAE grades

CTCAE grading within AE tables is displayed as "all grades", "Grade 1/2", "Grade 3/4" and "Grade 5". AEs with missing CTCAE or CTCAE grades not equal to 1 to 5 will be displayed under the category "all grades", but no category "missing grade" is displayed. A footnote is explaining that AEs with missing CTCAE or CTCAE grades not equal to 1 to 5 will be displayed under the category "all grades" and therefore the categories "Grade 1/2", "Grade 3/4" and "Grade 5" might not sum up to the category "all grades". A separate table will show

AEs leading to death. In this table no CTCAE grades will be shown. In the appendix (Section 16.1.9.2), the categorization "all Grades", "missing Grade", "Grade 1", "Grade 2", "Grade 3", "Grade 4" and "Grade 5" are used, but the "missing grade" column should only be displayed in case AEs with a missing CTCAE grade occured.

AE attributes "CTCAE Grade 1/2", "CTCAE Grade 3/4" and "CTCAE Grade 5" combined with drug relationship will be derived to avoid incorrect condensing. Consider, for instance, a patient with coincident drug-related abdominal pain with CTCAE Grade 1, and non-related vomiting with CTCAE Grade 3. Without the new attribute these AEs would be reported as drug-related Grade 3/4 under the SOC Gastrointestinal Disorder. With the new AE attribute these AEs would be excluded.

Additional AE attributes "Drug relationship combined with seriousness of the AE" and "Drug relationship combined with seriousness of the AE and CTCAE grade" is needed similarly to the AE attribute "CTCAE Grade 1/2", "CTCAE Grade 3/4" and "CTCAE Grade 5" combined with drug relationship respectively, as described above.

Frequencies of patients with AEs will be summarised by treatment, highest CTCAE grade, primary SOC and PT. Tables will be provided for patients with AEs of incidence > 10%, with drug-related AEs, with serious AEs (SAEs), with drug-related SAEs, with AEs leading to treatment discontinuation, with AEs leading to dose reduction, with protocol-specified significant AEs, with AEs leading to death, and with infusion-related reactions (IRRs).

7.8.1.3 Protocol-specified significant adverse events

Protocol-specified significant AEs are defined in the CTP, Section 5.2.2.1.

Infusion-related reactions (IRR)

Frequency of IRRs with CTCAE grade 3 or higher will be displayed in separate listings and tables where it will be differentiated between the reported AE term "Infusion-related reaction" and the symptoms of an IRR that are reported as AEs.

For patients at the beginning of this trial (up to the 9 mg dose cohort), the term IRR only or the symptoms of an IRR reported as AEs but not captured explicitly as symptoms of an IRR. For these patients, potential symptoms of an IRR can be only identified over pre-defined AE preferred terms (refer to Table 9.4:1).

For patients from following dose cohorts (including some patients of the 9 mg cohort), not only IRRs are reported with the AE term "Infusion-related reaction" but also their symptoms which are additionally marked as symptoms of an IRR.

A listing will show all patients with IRR episodes as well as reported symptoms of these IRRs. Furthermore symptoms of IRRs will also be displayed where it will be distinguished between symptoms marked as such and potential symptoms of an IRR (up to the 9mg dose cohort only).

The number of episodes of IRRs as well as the frequency of its symptoms and CTCAE grades will be displayed graphically for those patients where the symptoms of an IRR are reported as such.

The frequency of the AE "Infusion-related reaction" episodes will be displayed graphically by administration visit together with its CTCAE grade for all patients.

Tumour lysis syndrome

A frequency table displaying patients with clinical TLS (TLS reported as protocol-specified significant AE) will be provided. Additionally to cases of clinical TLS, laboratory TLS will be analysed (please refer to Section 7.8.2).

Any event that qualifies for DLT

Please refer to Section 5.2.1.1 of the CTP.

Drug-induced liver injury (DILI)

Please refer to Section 5.4.4. The frequencies of these protocol-specified significant AEs will be displayed in the CTR.

7.8.1.4 Adverse events by user-defined categories

A frequency table of AEs by user-defined categories, worst CTCAE grade, and preferred term as well as a frequency table of AEs by user-defined categories and worst CTCAE grade for the on-treatment period will be displayed.

7.8.1.5 Other significant AEs

Frequency tables of patients with AEs leading to dose reduction and AEs leading to treatment discontinuation will be provided by dose cohort and total, worst CTCAE grade, primary system organ class and preferred term for the on-treatment period.

7.8.2 Laboratory data

The analyses of laboratory data will be descriptive in nature and will follow the standard procedure laid down in the SOP_"Display and Analysis of Laboratory Data" (5). Patients will be counted under the initial treatment. The analysis of laboratory data will use the same 'analysing treatments' as described for the AEs, except for that the baseline laboratory value (as defined in Section 6.7) will be included in the 'on treatment' period. Patients having at least one post-baseline laboratory value will be displayed in the descriptive analyses. Patients with missing CTCAE grade at baseline or no baseline value but with post-baseline laboratory values will be displayed in the category "Missing CTCAE grade at baseline"

Single time courses by initial treatment will be used to display converted laboratory values over time by dose cohort. The graphs may be truncated if sufficient data is not available. These graphs will be displayed in Chapter 16.1.9.2 for the following parameters.

Haematology: haemoglobin, WBC count and platelets

Differentials: neutrophils (absolute count), absolute lymphocyte count, and natural killer (NK) cells

Enzymes: LDH

Clinically relevant abnormalities (as defined in Section 5.4.5.1) will also be summarised.

Descriptive statistics, including change from baseline, frequency of patients with transitions relative to the references range, will be provided. No post-study laboratory values will be considered. CTCAE grade for applicable laboratory parameters will be calculated according to CTCAE v4.0. The following outputs will be presented:

- Baseline, last value and difference from baseline
- Worst CTCAE grade experienced during the on-treatment period
- Transitions of the CTCAE grade from baseline to the worst lab values, from baseline to the last lab values, and from the worst to last values during the on-treatment period
- Possible clinically significant laboratory values

Note: For calculating the change in CTCAE grade from baseline, patients with a CTCAE grade of -9 (no CTCAE grade defined) will be treated as a CTCAE grade 0 for all analyses. In laboratory listings, the CTCAE grade is displayed as -9.

For Uric Acid and Hypokalemia, the CTCAE grade cannot always be assigned by the laboratory parameter itself as two different CTCAE grades have the same laboratory constellation, but are distinguished by additional clinical parameter. In this case a CTCAE grade of -1 will be assigned initially. Patients with a CTCAE grade of -1 will be treated as

- Grade 1 for Uric Acid
- Grade 1 for Hypokalemia

for all analyses. In laboratory listings, the CTCAE grade will be displayed as -1.

Patients with hepatic enzyme elevation will be tabulated. With respect to neutropenia, thrombocytopenia and leukopenia episodes the number of episodes and mean and median duration will be displayed. Additionally, laboratory values of special interest as described in Section 5.4.5 will be analyzed.

Additionally, a frequency table displaying number of patients with episodes of grade 4 neutropenia and concomitant AEs in the user-defined AE category (UDAEC) of any grade and grade 3/4 will be provided. In this context, concomitant AE is defined as AE with onset date within the neutropenia episode. The same table will be done for grade 3/4 episodes of neutropenia and concomitant AEs in the UDAEC of any grade and grade 3/4 will be done. The same applies for the display of patients with thrombocytopenia and bleeding events. For the definitions of neutropenia, thrombocytopenia and leukopenia episodes please refer to Section 5.2.5.2.

The prioritized laboratory values (see Section 5.4.5) will be displayed in Section 15 of the final CTR while all other laboratory parameters will be displayed in the Appendix of the CTR.

